4. PARTICIPANT SELECTION

4.1 Inclusion Criteria

4.1.1 At least two episodes of acute pancreatitis in the past 12 months. Acute pancreatitis is defined as any 2 of the following: (1) Typical upper abdominal pain; (2) Elevation in serum amylase or lipase ≥ 3 times upper limit of normal; (3) Features of acute pancreatitis on cross-sectional imaging.

4.1.2 Age ≥ 18 years.

4.1.3 ECOG performance status ≤ 1 (Karnofsky $\geq 70\%$; see Appendix B).

4.1.4 Participants must have acceptable organ, hepatic and renal function as defined below:

Leukocytes	$\geq 2,500/\text{microliter}$
Absolute neutrophil count	$\geq 1,500/\text{microliter}$
Platelets	$\geq 100,000/\text{microliter}$
Hemoglobin	$> 10 \text{ g/dL}$
Total bilirubin	$\leq 3 \times$ institutional upper limit of normal (ULN)
AST (SGOT)/ALT (SGPT)	$\leq 1.5 \times$ institutional ULN
Creatinine	$< 1.5 \text{ mg/dL}$

Patients whose lab levels meet the inclusion criteria by Screen 2 will be included in the trial.

4.1.5 Women of child-bearing potential must have a confirmed negative pregnancy test result prior to enrollment.

4.1.6 The effects of simvastatin on the developing human fetus at the recommended therapeutic dose are unknown. For this reason and because statins are known to be teratogenic, women of child-bearing potential must agree to use adequate contraception (hormonal or barrier method of birth control; abstinence) prior to study entry and for the duration of study participation. Should a woman become pregnant or suspect she is pregnant while participating in this study, she should inform her study physician immediately. It is not known whether simvastatin is excreted into human milk; however, a small amount of another drug in this class does pass into breast milk. Because statins have the potential for serious adverse reactions in nursing infants, women who receive treatment with simvastatin should not breastfeed their infants.

4.1.7 Ability to understand and the willingness to sign a written informed consent document and medical release.

4.1.8 Willing and able to comply with trial protocol and follow-up.

4.2 Exclusion Criteria

4.2.1 Prior or current use of statin medication, or current systemic use of gemfibrozil, cyclosporine, danazol, lomitapide, verapamil, diltiazem, dronedarone, amiodarone, amlodipine, ranolazine, or strong CYP3A4 inhibitors (e.g., itraconazole, ketoconazole, posaconazole, voriconazole, HIV protease inhibitors, boceprevir, telaprevir, erythromycin, clarithromycin, telithromycin, nefazodone, or cobicistat-containing products).

4.2.2 History of chronic myopathy

4.2.3 Current use of any other investigational agents

- 4.2.4 History of adverse effects, intolerance, or allergic reactions attributed to compounds of similar chemical or biologic composition to simvastatin (i.e., other statin medications).
- 4.2.5 Uncontrolled intercurrent illness including, but not limited to, ongoing or active infection, symptomatic congestive heart failure, unstable angina pectoris, cardiac arrhythmia, or psychiatric illness/social situations that would limit compliance with study requirements.
- 4.2.6 Women who are pregnant or breastfeeding. Pregnant women are excluded from this study because simvastatin is a lipid-lowering agent with the potential for teratogenic or abortifacient effects. Because there is an unknown but potential risk for adverse events in nursing infants secondary to treatment of the mother with simvastatin, breastfeeding should be discontinued if the mother is treated with simvastatin.
- 4.2.7 Presence of gallstones or hypertriglyceridemia (level greater than 800 mg/dl) that requires medical or surgical intervention. *Note: We will include patients who had an independent episode of pancreatitis after a cholecystectomy, but exclude patients who are candidates for cholecystectomy.*
- 4.2.8 History of pancreatic adenocarcinoma (at any time)
- 4.2.9 History of active malignancy in the past 2 years (excluding basal/squamous cell skin cancer or prostate cancer with a Gleason score 6 or less)
- 4.2.10 Known active infection with HIV
- 4.2.11 Concurrent illness, such as known psychiatric disorders or substance abuse (i.e., average alcohol consumption of more than 5 drinks per day), which in the opinion of the investigators would compromise either the patient or the integrity of the data
- 4.2.12 Lab results do not meet inclusion criteria 4.1.4 by Screen 2.
- 4.2.13 Recurrent pancreatitis episode is iatrogenic (endoscopic retrograde cholangiopancreatography (ERCP) induced)
- 4.2.14 Advanced chronic pancreatitis as determined by the following criteria: EUS score greater than or equal to 6, calcifications in combination with atrophy and/or dilation of ≥ 5 mm, or evidence of advanced chronic pancreatitis by computed tomography (CT) or magnetic resonance imaging (MRI) results in the past 12 months.

4.3 Inclusion of Women and Minorities

Both men and women and members of all races and ethnic groups are eligible for this trial.

4.4 Recruitment and Retention Plan

Patients with recurrent pancreatitis will be recruited for the study from the CSMC Pancreatic and Biliary Diseases Program, the KPMC Center for Pancreatic Care, the SU Gastroenterology and Digestive Health Clinic, and Presbyterian/Montefiore and Shadyside Hospitals at the UP Medical Center. Gastroenterologists at the four institutions jointly treat approximately 1,600 patients with acute pancreatitis annually, of whom approximately 600 (38%) are recurrent acute pancreatitis cases. We estimate that 40% (240) will not be eligible because they have not had at least two episodes of pancreatitis in the past 12 months, and that 40% will not be eligible due to current or prior statin use, presence of

gallstones, or other medical contraindications. We project that 120 potentially eligible patients will be approached for consent annually across four study sites (240 patients during the 24-month accrual period). Based on this patient population and the importance of our objectives to the gastroenterology community, **our recruitment goal of 30 patients** with two or more episodes of pancreatitis in the past 12 months is highly feasible. The sample size of 30 will include an estimated 14 women (10 white, 2 black, 2 Asian) and 16 men (11 white, 3 black, 2 Asian) with confirmed recurrent pancreatitis. Each of the investigators has substantial experience with patient recruitment and/or clinical trials of pancreatic diseases and will insure that our recruitment goals are met. Neither the repeated endoscopies nor the ePFT are considered barriers to recruitment as there is minimal risk (minor pain, discomfort, and few other sequelae) associated with the procedure. Healthy subjects have been subjected to cross-over studies of endoscopic and Dreiling tube pancreatic function tests, performed in tandem with a 1-week washout, and no procedure- or medication-related complications were reported [51]. Trial gastroenterologists will work closely with their gastroenterology teams in the recruitment effort.

Patients who are eligible for the trial based on the pre-screen eligibility review by the clinical research staff (initial determination of eligibility) will be provided with a study information packet that includes the IRB-approved study informed consent form and HIPAA authorization, and IRB-approved recruitment materials (each participating site will choose what materials to include). Patients will be encouraged to review the consent documents with family, friends, and/or other physicians. One of the trial gastroenterologists will review the study details and consent documents with interested pre-screen eligible patients after all clinical options have been presented to the patient. After the patient's questions have been answered, the gastroenterologist will obtain signatures on the consent documents. Written consent will be obtained before any research related procedures are initiated. After consent has been obtained, Screen 1, the secondary assessment of eligibility, will be conducted by trial gastroenterologists (review of computed tomography (CT) and magnetic resonance imaging (MRI) results and confirmation of recurrent pancreatitis). Consented patients who are eligible after Screen 1 will undergo Screen 2 (final determination of eligibility to rule out advanced chronic pancreatitis and pregnancy) within 8 weeks after consent. Screen 2 eligible/consented patients will be registered and randomized to the study drug. Study Visit 1 (Baseline measurements), the beginning of the intervention (study agent dispensed), will occur 0-14 days after Screen 2.

Research visits, scheduled at the participating clinic, will coincide whenever practicable with usual care to reduce travel time and increase compliance with the study protocol. Participants will receive \$50 when they complete the Screen 2 testing and \$150 at the time they complete each study visit for their time, transportation, parking, and other expenses related to the study. Participants who complete the entire study – the Screen 2 testing, and three study visits – will receive \$500.

Compensation schedule

Screen 2	Study Visit 1	Study Visit 2	Study Visit 3
\$50	\$150	\$150	\$150

Study visits will be scheduled at 3 months (\pm 1 month) and 6 months (\pm 1 month) to avoid protocol violations. A day or two prior to the scheduled follow-up visit, the participant will be contacted by telephone to confirm or reschedule his/her visit. Patients who develop intercurrent pancreatitis will receive usual medical care by their gastroenterologist, and their next study visit will be rescheduled if necessary. The study coordinator will have a database which tracks active participants who do not have a scheduled visit or who have missed their targeted visit date. Study visits will be rescheduled for up to 2 months until the participant is considered lost to follow-up.

5. AGENT ADMINISTRATION

Intervention will be administered on an outpatient basis. Reported adverse events (AEs) and potential risks are described in Section 6.2.

5.1 Dose Regimen and Dose Groups

Thirty participants with recurrent pancreatitis will be randomized into one of 2 groups: 20 participants will receive 40 mg simvastatin per day and 10 participants will receive a placebo identical in color, consistency, and appearance to simvastatin 40 mg. Simvastatin and placebo will be provided as over-encapsulated tablets. Dosing will extend for 6 months.

- Agent(s): Simvastatin and placebo
- Daily dose(s) and regimen(s) for each agent: One 40 mg capsule per day
- Duration for each agent: Daily treatment for 6 months

The usual recommended dose of simvastatin is 10-40 mg/day, and the toxicity and tolerability are comparable for 20 mg and 40 mg [8].

5.2 Study Agent Administration

Patients will self-administer the 40 mg capsule of simvastatin or placebo daily in the evening. Patients will be instructed to take the study agent at bedtime or with an evening meal. Each participant will be given 1 bottle of 120 capsules at Study Visit 1 and 1 bottle of 120 capsules at Study Visit 2 (Month 3).

5.3 Run-in Procedures

None.

5.4 Contraindications

Patients are advised not to consume any form of grapefruit (e.g., juice, fruit, grapefruit seed extract, dietary supplements containing grapefruit) while on simvastatin as grapefruit may increase the blood levels of simvastatin [52]. Participants enrolled in the study will be instructed to avoid all forms of grapefruit.

The combined use of simvastatin with systemic formulations of gemfibrozil, cyclosporine, danazol, lomitapide, verapamil, diltiazem, dronedarone, amiodarone, amlodipine, ranolazine, or strong CYP3A4 inhibitors (e.g., itraconazole, ketoconazole, posaconazole, voriconazole, HIV protease inhibitors, boceprevir, telaprevir, erythromycin, clarithromycin, telithromycin, nefazodone, and cobicistat-containing products) is contraindicated due to an increased risk for myopathy. Patients will be screened for contraindications to simvastatin prior to enrollment in the study. Patients with known active infection with HIV will be excluded from the study. Patients will be advised not to use contraindicated medications during the study and will be excluded if systemic use of any contraindicated medication is unavoidable. Concomitant medications will be reviewed at study visits and during follow-up telephone calls. Participants will be closely monitored for symptoms and side effects to the study drug and will be instructed to call the study doctor immediately if they have a serious adverse reaction.

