5.6 Dose Modification

No dose modifications are planned. The study agent will be stopped in the event of an AE \geq grade 3 considered possibly, probably, or definitely related to the study agent. The study agent will be restarted after resolution. One of the common side effects of statin medication is myalgia (muscle pain with normal creatine phosphokinase (CPK) level), and rarely this is associated with statin myopathy (muscle weakness or other muscle injury with or without elevation in CPK level). In randomized controlled trials of standard dose statin therapy, the risk is very low (<1%). We will measure levels of CPK in the blood drawn at the first study visit to establish a patient-specific reference for this indicator of muscle toxicity. During the trial, if the participant reports unexplained muscle pain or weakness, CPK will be tested again to check for elevation. The study agent will be temporarily discontinued in subjects experiencing grade 1 or greater myopathy (unexplained muscle symptoms *and* creatine phosphokinase (CPK) > 2.5 times institutional ULN) or hepatotoxicity (ALT or AST > 1.5 times institutional ULN) that is considered possibly, probably, or definitely related to the study agent. Resolution of myopathy or hepatotoxicity will be evaluated with follow-up laboratory blood tests 4 weeks after the elevated levels occur. If the lab test results are still elevated after 4 weeks, the study agent will be discontinued permanently and the participant's primary care physician will be notified of the abnormal tests. If the lab test results return to normal levels, participant will go back on the study agent.

Because dose modification could lead to lack of dose homogeneity that may impair the research objectives, we will stop the intervention in patients who initiate drugs that require dose modifications of simvastatin below 40 mg: lomitapide, verapamil, diltiazem, dronedarone, amiodarone, amlodipine, or ranolazine.

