6.2 Reported Adverse Events and Potential Risks

The most common (incidence $\geq 5.0\%$ patients) reported adverse events (AEs) are upper respiratory infection, headache, abdominal pain, constipation, and nausea. Other AEs reported in clinical trials ($<5\%$) were diarrhea, rash, dyspepsia, flatulence, and asthenia.

Persistent increases in serum transaminases (to more than 3 x ULN) have occurred in approximately 1% of patients who received simvastatin in clinical studies. When drug treatment was interrupted or discontinued in these patients, the transaminase levels usually fell slowly to pretreatment levels. The increases were not associated with jaundice or other clinical signs or symptoms. It is recommended that liver function tests be performed before the initiation of treatment, and thereafter when clinically indicated.

Simvastatin occasionally causes myopathy manifested as muscle pain, tenderness or weakness with creatine kinase above 10 x ULN. Myopathy sometimes takes the form of rhabdomyolysis with or without acute renal failure secondary to myoglobinuria, and rare fatalities have occurred. Predisposing factors for myopathy include advanced age (≥ 65 years), female gender, uncontrolled hypothyroidism, and renal impairment. The risk of myopathy, including rhabdomyolysis, is dose related. The risk of myopathy and rhabdomyolysis is increased by high levels of statin activity in plasma. Simvastatin is metabolized by the cytochrome P450 isoform 3A4 (CYP3A4). Certain drugs which inhibit this metabolic pathway can raise the plasma levels of simvastatin and may increase the risk of myopathy. These include itraconazole, ketoconazole, posaconazole, voriconazole, the macrolide antibiotics erythromycin and clarithromycin, and the ketolide antibiotic telithromycin, HIV protease inhibitors, boceprevir, telaprevir, the antidepressant nefazodone, cobicistat-containing products, or grapefruit products. Combination of these drugs with simvastatin is contraindicated. If short-term treatment with strong CYP3A4 inhibitors is unavoidable, therapy with simvastatin must be suspended during the course of treatment.

Increases in HbA1c and fasting serum glucose levels have been reported with HMG-CoA reductase inhibitors, including simvastatin.

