8.3 Off-Agent Criteria

Participants may stop taking study agent for the following reasons: completed the protocol-prescribed intervention, adverse event or serious adverse event, inadequate agent supply, noncompliance, concomitant medications, or medical contraindication. Participants who experience complications of pancreatitis or develop intercurrent pancreatitis during the study will be instructed to continue taking the study agent unless they are unable to take oral medications. The study agent will be resumed as soon as they are able to tolerate oral medications. Participants will continue to be followed, if possible, for safety reasons and in order to collect endpoint data according to the schedule of events.

As described in section 7.5, clinical research staff will make follow-up telephone calls to the participants on days 30 ± 7 , 60 ± 7 , and 90 ± 7 after the participant discontinues the study agent to assess symptoms and adverse events. Standard of care data (medical history, laboratory test results, concomitant medications, imaging results) will continue to be collected via review of the participant's electronic medical record at the time points specified in the Schedule of Time and Events. If feasible, we will conduct a research visit to collect final measurements for participants who permanently discontinue the study agent early. An end-of-study research visit will be conducted 6 months after initiation of the statin intervention (Study Visit 3). The blood collections for clinical labs and banked samples future research, and the follow-up risk questionnaire will not be done. The following procedures will be performed during the end-of-study visit:

1. Review medical history, medications, and laboratory test results
2. Vital signs assessment, measurement of weight, and symptom assessment
3. ECOG performance status

4. Pregnancy test for women of child-bearing potential. Women who have had a hysterectomy, both ovaries removed, or a tubal ligation will not be required to have a pregnancy test.

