13.5 Secondary Objectives, Endpoints, Analysis Plans

For secondary endpoints, we will consider D(T) and D(P) as well as percent change relative to baseline as well, namely, D (T)/B (T) and D (P)/B (P). For all secondary variables, we will use descriptive statistics and graphics at 3 months and at 6 months, as well as study random effects regression trends along the timeline Baseline → 3 months → 6 months for further hypotheses generation. In particular, we will look into cytokines, chemokines, and adhesion molecules and quality of life scores from the QLQ-C30 and QLQ-PAN28(CP) assessment after possible log-transformation of continuous data. In particular, we will be interested in the relation between a) pairs of secondary variables and differences D=After-Before in pairs of secondary variables in the Treatment group, b) same as a) but in the control group, c) comparing pairwise changes between the Treatment and the Control groups, and d) relationship of secondary outcomes with recurrent pancreatitis. In this way, we will be able to study co-dependence among various secondary variables and their possible relationship with recurrent pancreatitis. We will thus fit various regression models, estimate relevant parameters (e.g., intercept, slope) and explore the apparent magnitudes of change in these parameters in the treatment and the control group.

Analyses will be performed with Stata software. All analyses will be conducted on an intention to treat basis (all randomized participants will be included in the assigned group) and will begin with univariate cross-sectional statistics for profiling the study population and bivariate tabulations as a preliminary step to possible model building. We will not control for overall Type I error due to small number of

observations and the preliminary nature of the study.

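### Sections 5.4 and 6.2 conflict on an unavoidable short course of a strong CYP3A4 inhibitor, the 5.6 stop list is narrower than the 5.4 list, and *excluded* in 5.4 is undefined for randomized participants

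*Combined protocol and SAP*

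**What the plan says.** Four parts of the protocol bear on a participant who needs an interacting drug.

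- **5.4 Contraindications.** The contraindication covers "The combined use of simvastatin with systemic formulations of gemfibrozil, cyclosporine, danazol, lomitapide, verapamil, diltiazem, dronedarone, amiodarone, amlodipine, ranolazine, or strong CYP3A4 inhibitors". Patients are told to avoid these drugs while in the study and "will be excluded if systemic use of any contraindicated medication is unavoidable".
- **5.6 Dose Modification.** To keep the dose uniform, "we will stop the intervention in patients who initiate drugs that require dose modifications of simvastatin below 40 mg". Seven drugs are then named.
- **6.2 Reported Adverse Events and Potential Risks.** "If short-term treatment with strong CYP3A4 inhibitors is unavoidable, therapy with simvastatin must be suspended during the course of treatment".
- **8.3 Off-Agent Criteria.** The reasons for stopping the agent include "inadequate agent supply, noncompliance, concomitant medications, or medical contraindication". After that, "Participants will continue to be followed, if possible, for safety reasons and in order to collect endpoint data". If feasible, a participant who permanently stops early has a six-month visit that includes the ePFT.

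On the analysis side, 13.5 states that "All analyses will be conducted on an intention to treat basis", with every randomized participant kept in the assigned group. Section 13.8 evaluates the primary endpoint in all randomized participants.

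**The concern.** A site coordinator who learns on a four-weekly call that a participant has been prescribed, say, clarithromycin finds one outcome in 5.4 and another in 6.2. The section that governs changes to the agent, 5.6, does not mention the drug class. Section 5.5 asks only for documentation, and 7.3.2 includes a concomitant-medication review without attaching an action to it.

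Two things are at stake. The first is safety handling. Section 5.4 gives myopathy as the reason for the contraindication, and CPK is scheduled only at Study Visit 1, with a repeat only if muscle symptoms are reported. Sites should not have to choose between passages. The second is retention. If *excluded* is taken to mean off study, a randomized participant may never have the Visit 3 ePFT, and an intention-to-treat statement cannot recover a measurement that was not made.

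**Working it through.** This is a check of text against text. The plan gives no rate of starting a contraindicated drug, so there is no figure to reproduce.

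**Step 1: coverage by drug group.** Section 5.4 names ten drugs and one class. Section 5.6 names seven drugs, all among those ten, so 10 − 7 = 3 named drugs are missing, as is the class.

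| Drug group | 5.4 | 5.6 | 6.2 |
|---|---|---|---|
| The seven drugs named in 5.6 | excluded if unavoidable | intervention stopped | not addressed |
| Gemfibrozil, cyclosporine, danazol | excluded if unavoidable | not listed | not addressed |
| Strong CYP3A4 inhibitors | excluded if unavoidable | not listed | suspended during a short unavoidable course |

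**Step 2: where the rules conflict.**

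- Strong CYP3A4 inhibitors have two rules for one trigger. Suspension for the length of a course implies that the agent resumes; exclusion does not.
- For the seven drugs in 5.6 the two wordings differ but are compatible if *excluded* means off agent.
- The other three drugs are covered by 5.4 alone, so for them the meaning of *excluded* decides everything.

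**Step 3: what *excluded* can mean after randomization.** The sentence before it in 5.4 uses the same word for keeping patients with active HIV infection out of the study. Sections 7.2.2 and 7.2.3 use it for removal from the trial at screening. Yet the 5.4 sentence is tied to drug use during the study.

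A route to removal also exists. Study Visit 2 (7.3.1) re-checks the inclusion and exclusion criteria, criterion 4.2.1 excludes current systemic use of these same drugs, and 8.4 lists ineligibility and protocol violation as off-study reasons. A site that follows this route takes a randomized participant off study. A site that follows 8.3 takes the same participant off agent and continues to collect endpoint data. Only the second course agrees with 13.5 and 13.8.

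**The case against.** The best defence is that 5.4 is an eligibility rule. It speaks of patients, follows directly on pre-enrollment screening, and uses a word that the protocol mostly reserves for screening. Section 6.2 is risk information, refers to simvastatin rather than the study agent, and covers only short courses of one class. On that reading nothing conflicts. This does not settle the matter: the 5.4 sentence concerns use during the study, the 6.2 wording is mandatory, and the Visit 2 re-check carries the exclusion criteria past randomization. The text is ambiguous, and that is enough to need repair.

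The defence does dispose of several stronger readings that a reader might infer.

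- **Three competing rules for one drug.** The table shows none. Section 5.6 limits itself to drugs that call for a lower simvastatin dose, so its silence on other drugs is a gap and not an instruction to continue. Section 8.3 also allows the agent to be stopped for concomitant medication.
- **No stated action for a macrolide course.** Erythromycin and clarithromycin are named in both 5.4 and 6.2, and each section gives an action. The trouble is that the actions differ.
- **Retention in the analysis is contradictory throughout.** Sections 8.3, 13.5 and 13.8 agree with one another. The contradiction arises only if *excluded* is read as removal from the study.
- **A calculable loss of power.** No prescription rate is given. The plan already allows for 4 + 2 = 6 dropouts (30 − 6 = 24), and an excluded participant could be one of those six.

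**Conclusion.** The point holds in three parts. Sections 5.4 and 6.2 give different outcomes for an unavoidable short course of a strong CYP3A4 inhibitor. The 5.6 list omits three named drugs and one class that 5.4 calls contraindicated. *Excluded* in 5.4 is undefined for randomized participants, and one natural reading contradicts 8.3, 13.5 and 13.8.

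The first and third parts rest on 5.4 applying after randomization, which its wording allows but does not spell out. The size cannot be given as an expected number of participants or a change in power. As a scale only, one post-randomization removal would be 1/20 = 5% of those randomized to simvastatin or 1/10 = 10% of those randomized to placebo. The sponsor should correct this because the text permits different handling across four sites and avoidable loss of the primary endpoint. Which action on the agent is right is a clinical question that this review does not answer.

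**What to change.** 1. Reconcile 5.4, 5.6 and 6.2 into one rule that covers every drug and class in the 5.4 list, and have the other sections refer to it. The agent action for each is for the sponsor and investigators to decide.
2. In 5.4, limit *excluded* to patients not yet randomized. For randomized participants, refer to 8.3: whatever happens to the agent, they stay in follow-up, have the Visit 3 ePFT where feasible, and are analysed as randomized.
3. State in 7.3.1 and 8.4 that starting a listed drug after randomization is handled under 8.3 and is not in itself a reason to go off study.

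The cost is a wording amendment with the usual sponsor and IRB approval. It needs no new procedures, visits or participants.
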